## 9.2.9. Actual Treatment

The subjects' actual treatment will be derived from exposure data provided by Clinical Operations. If a subject's actual treatment is the same as the assigned treatment, then actual treatment is the assigned treatment. If a subject receives a study treatment that is different from the assigned treatment for the entire time of treatment, then actual treatment is the different treatment (the treatment actually received).

## 9.2.10. Cardiac Scan Modalities (ECHO/MUGA)

The same modality (ECHO or MUGA) for determining cardiac scan data (e.g., left ventricular ejection fraction (LVEF)) should be used to follow a subject throughout the study. The absolute change from baseline values will not be calculated for any subjects where the post-baseline value was determined by a cardiac scan modality that is different than the one used to determine baseline value.

## 9.2.11. Derived and Transformed Variables

See Section 11 for details on analyses for overall response, overall response rate, duration of response.

#### **Deriving and Summarizing Pharmacokinetic Parameters**

See Section 13 for derivation of PK parameters.

#### **ECG Correct QT Intervals**

The following parameters will be derived if applicable. They are derived to the same number of decimal places as the raw data.

Variable	Description	Algorithm
RR	RR interval	
 
If QTcB is machine read and QTcF is not provided, then: RR = [(QT/QTcB)^(2)]*1000
 
If QTcF is machine read and QTcB is not provided, then: RR = [(QT/QTcF)^(3)]*1000
 
If ECGs are manually read, the RR value preceding the measured QT interval should be a collected value Do Not Derive.
 

QTcB	QTc interval, using Bazett's correction	
 
If not provided in dataset, derive:
 
QTcB = QT / ((RR/1000)^1/2), where RR is in msec
 

QTcF	QTc interval, using Fredericia's correction	
 
If not provided in dataset, derive:
 
QTcF = QT / ((RR/1000)^1/3), where RR is in msec
 

### 9.3. Study Time Periods

#### 9.3.1. Time in Relation to Treatment

Adverse events, serious adverse events, death, laboratory data, vitals, ECG, ECHO/MUGA, and questionnaire data (ECOG), will be assigned to the study time periods defined below. Partial dates will be imputed into full dates, if applicable, for slotting data to the appropriate categories below (see Section 9.2). Flag variables (time in relation to study treatment) indicating the study time periods will be added to these datasets.

**Pre-therapy** is defined as the time prior to the subject's first dose of study treatment.

**On-therapy** is defined as the time from first dose of study treatment to the last dose date of study treatment + 28 days.

**Post-therapy** is defined as any time at least 45 days or 5 half lives (whichever comes later) after the last dose of study treatment.

Some datasets include the first dose day as On-therapy and some exclude the first dose date as On-Therapy. The first dose day and time (Day 1) is considered pre-therapy for ECOG, ECG, vital signs, liver events, and lab tests, if the time is before first dose. The

first dose day (Day 1) is considered to be On-therapy for adverse events and concomitant medications.

### 9.3.2. Study Time Periods for Concomitant Medications

Concomitant Medication start and end dates will be assigned to study time periods in relation to first dose of study treatment as defined below. The start date references time flag variables and end date reference time flag variables will be added to the concomitant medications dataset.

- Start relative to treatment: Assign to 'BEFORE' if start date is prior to study treatment start date or if subject has not taken any study treatment, or start date is missing and end date is before study treatment start date. Else assign to 'DURING' if the start date falls into the on-therapy period as defined above or if subject is ongoing (not all study treatment discontinuation records completed) or start date is missing. Else assign to 'AFTER' if start date is after the on-therapy period.
- End relative to treatment: Assign to 'BEFORE' if end date is prior to study treatment start date or if subject has not taken any study treatment. Else assign to 'DURING' if start date falls into the on-therapy period or if subject is ongoing (not all study treatment discontinuation records completed). Else assign to 'AFTER' if start date is after the on-therapy period or (end date is missing and start relative to treatment='AFTER').

Concomitant medication start relative to treatment and end relative to treatment flags are used to select data to include in the Concomitant Medication summaries as follows:

- Summary of Concomitant Medications: This summary will contain medications including those with start date prior to study treatment start date and continue (missing end date or end date after study treatment start date) on therapy. Note that any medications with start date and end date prior to study treatment start date will be excluded. In addition, any medication that was started during post-therapy will be excluded. Include concomitant medication records where start relative to treatment in ('BEFORE','DURING') and end relative to treatment in ('DURING','AFTER').
- Summary of Concomitant Medications with On-Therapy Onset: This summary will contain medications with start date after study treatment start date. In addition, any medication that was started during post-therapy (see above for definition of post-therapy) will be excluded. Include concomitant medication records where start relative to treatment in ('DURING') and end relative to treatment in ('DURING','AFTER').

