# 19.1.1. Study Population

### **Tables**

No.	Population	IDSL No. / Example Shell	Title	Additional Programming Notes	Deliverable
9.1	All Treated	ES6	Summary of Study Eligibility in Screening	Including screening failure and reason of failure	SAC
9.2	All Treated	POP1	Summary of Analysis Populations	Footnote subject ID and excluded population	SAC
9.3	All Treated	DV1A	Summary of Protocol Deviation	Add a column for Total	SAC
9.4	All treated	ES1	Summary of Subject Disposition		SAC
9.5	All treated	DM1	Summary of Demographic Characteristics	Include height, weight and BMI at screening or baseline, and country; add age by categories.	SAC
9.6	All treated	DM5	Summary of Race		SAC
9.7	All treated	LA1	Summary of Disease Characteristics at Baseline		SAC
9.8	All Treated	CM8	Summary of Concomitant Medication by Ingredient for Medication Started prior Study Treatment	only for medications start prior to study and continue during study	SAC
9.9	All Treated	CM8	Summary of Concomitant Medication by Ingredient	Including medications start on or after date of first dose; excluding ones taken post therapy period.	SAC
9.10	All Treated	AC3	Summary of Prior Anti-Cancer Therapies	/arenv/arprod/gsk2636771/p3b115717/sac /drivers/t_ac3.sas	SAC
9.11	All Treated		Summary of Baseline ECOG Performance Status	/arenv/arprod/gsk2636771/p3b115717/sac /drivers/t_ecog.sas	SAC
9.12	All Treated	PS4A/ Shell	Summary of Change from Baseline in ECOG Performance Status		SAC

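### The concomitant-medication end flag tests the start date, so for subjects off treatment, drugs begun before first dose and continued get no flag and leave the overall summary

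*SAP*

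**What the plan says.** SAP 9.3.2 gives every medication record a start flag and an end flag.

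- **Start flag.** "Assign to 'BEFORE' if start date is prior to study treatment start date or if subject has not taken any study treatment". A record with no start date is also BEFORE if it ended before treatment. DURING covers a start in the on-therapy period, a subject still ongoing, or any other missing start date. A later start is AFTER.
- **End flag.** Three clauses are applied in order. First: "Assign to 'BEFORE' if end date is prior to study treatment start date or if subject has not taken any study treatment". Second: "Else assign to 'DURING' if start date falls into the on-therapy period or if subject is ongoing". Third: "Else assign to 'AFTER' if start date is after the on-therapy period or (end date is missing and start relative to treatment='AFTER" (the quotation stops just before the closing marks).
- **On-therapy period (SAP 9.3.1).** It "is defined as the time from first dose of study treatment to the last dose date of study treatment + 28 days".

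The Summary of Concomitant Medications keeps records with "start relative to treatment in ('BEFORE','DURING') and end relative to treatment in ('DURING','AFTER" (closing marks again omitted). The On-Therapy Onset summary requires a start flag of DURING and the same two end-flag values.

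On intent, the first summary's own description says "This summary will contain medications including those with start date prior to study treatment start date and continue". It spells out that continuing means an end date that is missing or later than treatment start. SAP 10.4 plans a separate summary of drugs with pre-therapy onset. The programming note to Table 9.8 in SAP 19.1.1 is "only for medications start prior to study and continue during study".

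**The concern.** A flag meant to locate the end of a medication looks at an end date only in its BEFORE clause. The DURING and AFTER clauses look at the start date. A drug begun before first dose can satisfy neither, so its end flag is never set unless the drug also stopped before treatment or the subject is still ongoing.

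Background medication is what a reader of a first-in-human safety report wants to see beside the adverse events. Protocol 10.1 permits analgesics, anticoagulants and antiplatelet agents, and protocol 10.2 permits low-dose corticosteroids for chronic conditions. Infusion and allergic reactions are events of special interest in SAP 12.3. If long-standing medication falls out of the summary that claims to include it, that context is missing and nothing in the output shows the gap.

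**Working it through.** There is no planned figure to reproduce. The check is a truth table: the start flag, end flag and two selection filters of SAP 9.3.2 applied literally to every feasible pair of dates. The subject is treated and has complete discontinuation records, so is no longer ongoing. The last two columns put the end date in place of the start date in the DURING and AFTER clauses and change nothing else. In the *kept* columns, A is the Summary of Concomitant Medications and B is the On-Therapy Onset summary.

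| Start date | End date | Start flag | End flag as written | Kept | End flag, word swap only | Kept |
|---|---|---|---|---|---|---|
| before | before | BEFORE | BEFORE | – | BEFORE | – |
| before | on therapy | BEFORE | none | – | DURING | A |
| before | after | BEFORE | none | – | AFTER | A |
| before | missing | BEFORE | none | – | none | – |
| on therapy | on therapy | DURING | DURING | A, B | DURING | A, B |
| on therapy | after | DURING | DURING | A, B | AFTER | A, B |
| on therapy | missing | DURING | DURING | A, B | none | – |
| after | after | AFTER | AFTER | – | AFTER | – |
| after | missing | AFTER | AFTER | – | AFTER | – |
| missing | before | BEFORE | BEFORE | – | BEFORE | – |
| missing | on therapy | DURING | none | – | DURING | A, B |
| missing | after | DURING | none | – | AFTER | A, B |
| missing | missing | DURING | none | – | none | – |

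Reading the table:

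1. **Begun before and continued (rows 2 to 4).** All 3 cases have no end flag as written and are lost from A. The section's description says all 3 belong there.
2. **Missing start date, not ended before treatment (rows 11 to 13).** All 3 cases carry a start flag of DURING but no end flag, so they are lost from both A and B.
3. **Unflagged in total.** 3 + 3 = 6 of the 13 feasible combinations. These are combinations, not records; the documents give no record counts.
4. **A and B become the same.** As written, both filters keep only the three rows with a start on therapy (rows 5 to 7), so two summaries described differently select identical records.
5. **A mislabel without consequence.** A drug started on therapy and ended afterwards is flagged DURING rather than AFTER, but it is kept either way.
6. **The word swap alone is not enough.** Rows 4 and 13 stay unflagged. Row 7, which the present text keeps, would become unflagged and be lost. That leaves 3 of 13 combinations with no flag, all with a missing end date.

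For a subject who is still ongoing, the second clause assigns DURING and the records begun before and continued are kept in A. SAP 4.2 places the final analysis after all subjects have completed the study and the database is frozen, so that route should save few records or none.

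**The case against.** The other side has several fair points.

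- **Table 9.8.** A reader might infer that Table 9.8 would be empty, with all its intended records lost. The documents do not support that as a certainty. SAP 9.3.2 ties the flags to two named summaries, and Table 9.8 is neither. Its selection rule is its own programming note, and SAP 10.4 selects by onset date plus use at some point in the on-therapy window. The table is emptied, or nearly so, only if the programmer builds it from these flags.
- **Table 9.9.** A reader might also take a table holding only drugs begun on therapy as a symptom of the error. For Table 9.9 it is the design: its note restricts it to medications started on or after first dose. SAP 19.1.1 lists no table combining drugs begun before and during treatment, so the summary that fails has no exact counterpart in the display list.
- **Loss from the report as a whole.** A reader might infer that long-standing medications vanish from reporting. They do not. ICH Listing 12 (SAP 19.1.7) lists concomitant medications for the All Treated population, with no flag filter in its note.
- **Intent is plain and derivations live elsewhere.** SAP 9.2 leaves full derivations to separate dataset specifications, which are not among these documents. A programmer may already have corrected the slip.

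The first three points limit the consequence and stand. The last does not cure the text. Section 9.3.2 is written as an executable rule with literal flag values, it contradicts its own description, and whether the specifications repair it cannot be verified here. SAP 8.1 also requires departures from the plan to be identified in the final report, so a silent repair would itself be a departure.

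**Conclusion.** The point holds. For subjects no longer ongoing, the end-flag rule in SAP 9.3.2 leaves all 3 begun-before-and-continued cases unflagged and removes them from the Summary of Concomitant Medications, against the section's stated intent. It also removes from both 9.3.2 summaries the 3 cases with a missing start date that did not end before treatment.

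This assumes that the rule is programmed as written and that subjects have complete discontinuation records at the final analysis. Any effect on Table 9.8 depends on the further, undocumented assumption that it uses these flags. The number of records affected cannot be estimated from the documents.

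The damage is limited to descriptive concomitant-medication summaries. No efficacy result, futility rule or error rate is involved, and the subject-level listing remains complete. It is a rule that gives a wrong result and should be corrected, but it does not threaten the study's conclusions.

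**What to change.** Rewrite the end flag in SAP 9.3.2 as follows:

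1. BEFORE: unchanged.
2. DURING: the **end** date falls in the on-therapy period, or the subject is ongoing.
3. AFTER: the **end** date is later than the on-therapy period, or the end date is missing and the start flag is AFTER.
4. New clause: if the end date is missing and the start flag is BEFORE or DURING, assign DURING or AFTER. Choose one and state it. Do not introduce a separate value for ongoing medication, because both filters accept only DURING and AFTER and would reject the records the clause is meant to keep.

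With clause 4, rows 4, 7 and 13 of the table are flagged and no feasible combination is left without a value. Row 4 then enters the overall summary only; rows 7 and 13 enter both.

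The notes to Tables 9.8 and 9.9 should also state which flag values each uses, so that both tables and the 9.3.2 summaries select the records the text describes. If the dataset specifications already contain a correct derivation, the SAP text should be brought into line with them.

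Cost: a paragraph of wording, two table notes and one derivation to reprogram or confirm. No additional data are needed.

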## 9.4. Values of Potential Clinical Importance

#### 9.4.1. Laboratory Parameters

Reference ranges for all laboratory parameters collected throughout the study are provided by the laboratory. A laboratory value that is outside the reference range is considered either high abnormal (value above the upper limit of the reference range) or low abnormal (value below the lower limit of the reference range). Note: a high abnormal

or low abnormal laboratory value is not necessarily of clinical concern. The laboratory reference ranges will be provided on the listings of laboratory data. Clinical laboratory test results outside of the reference range will be flagged in the listings.

To identify laboratory values of potential clinical importance, National Cancer Institute Common Terminology Criteria for Adverse Events (NCI-CTCAE v4.0) will be used to assign grades to the relevant laboratory parameters. NCI-CTCAE v4.0 can be found at http://ctep.cancer.gov/reporting/ctc.html.

For laboratory data which are not listed in the NCI CTCAE v4.0, a summary of values outside the normal range will be provided.

### 9.4.2. ECG Parameters:

The following criteria will be used to flag electrocardiogram (ECG) values that are values of potential clinical importance:

To identify QTc (Bazett's or Fridericia's) values of potential clinical importance, NCI-CTCAE v4.0 will be used to assign grades (see adverse event 'Electrocardiogram QT corrected interval prolonged'). Note that there is a slight inconsistency between CTCAE v4 and ICH E14 (Absolute QTc interval prolongation). It was decided to align with CTCAE for the oncology standard categories.

ECG Parameter	Potential Clinical Importance (PCI) Range	Unit
Absolute QTcF [QTcB]	$\geq$ 450 to <481 (Grade 1)	Msec
interval	$\geq$ 481 to <501 (Grade 2)	
	≥501 (Grade 3)	
Increase from baseline	Increase of $\geq$ 31 to $\leq$ 60	Msec
QTcF [QTcB]	Increase of >60	

The following criteria will be used to flag other ECG values that are values of potential clinical importance:

ECG Parameter	Potential Clinical Importance (PCI) Range	Unit
PR interval	<110 (L) and >220 (H)	Msec
QRS interval	<75 (L) and >110 (H)	Msec

#### 9.4.3. Vital Signs

To identify heart rate values of potential clinical importance, NCI-CTCAE v4.0 will be used to assign categories that align with the grades for 'Sinus bradycardia', 'Sinus tachycardia', 'Supraventricular tachycardia', and 'Ventricular tachycardia'.

The following criteria will be used to flag vital sign values that are values of potential clinical importance:

Vital Sign Parameter	Potential Clinical Importance (PCI) Range	Unit
Decrease from baseline Heart Rate	Decrease to <60	bpm
Increase from baseline Heart Rate	Increase to >100	bpm

To identify blood pressure values of potential clinical importance, NCI-CTCAE v4.0 will be used to assign categories that align with the grades for 'Hypertension'.

Vital Sign Parameter	Potential Clinical Importance (PCI) Range	Unit
Increase from baseline	$\geq 120 \text{ to } < 140 \text{ (Grade 1)}$	mmHg
Systolic Blood Pressure	$\geq$ 140 to <160 (Grade 2)	
	≥160 (Grade 3)	
Increase from baseline	≥80 to <90 (Grade 1)	mmHg
Diastolic Blood Pressure	$\geq$ 90 to <100 (Grade 2)	
	≥100 (Grade 3)	

To identify temperature values of potential clinical importance, NCI-CTCAE v4.0 will be used to assign categories that align with the grades for 'Hypothermia' and 'Fever'.

Vital Sign Parameter	Potential Clinical Importance (PCI) Range	Unit
Increase from baseline	Increase to ≥38	Degrees
temperature		С
Decrease from baseline	Decrease to ≤35	Degrees
Diastolic Blood Pressure		С

## 9.4.4. Left Ventricular Ejection Fraction

The following criteria will be used to flag left ventricular ejection fraction (LVEF) values that are values of potential clinical importance:

To identify LVEF values of potential clinical importance, NCI-CTCAE v4.0 will be used to assign categories that align with the grades for 'Ejection fraction decreased'.

LVEF Parameter	Potential Clinical Importance (PCI) Range	Unit
Absolute change from	• No change or any increase	%
baseline LVEF	Any decrease	
	$\circ$ >0-<10 decrease	
	o 10-19 decrease	
	$\circ \geq 20$ decrease	
	○ $\geq$ 10 decrease and $\geq$ LLN	
	$\circ \geq 10$ decrease and below LLN	
	$\circ \geq 20$ decrease and $\geq LLN$	
	$\circ \geq 20$ decrease and below LLN	
Relative to change from	• $\geq 20$ decrease and $\geq LLN$	
baseline LVEF	• ≥20 decrease and below LLN	

# 10. STUDY POPULATION

Unless otherwise stated, all tables and listings in this section will be based on All Treated Subjects population, and all summaries and data listings will use treatment labels as specified in Section 7.

The lists of displays for Study Population, including population to use for each display, are shown in Section 19 of the RAP.

## 10.1. Disposition of Subjects

A summary of the number of subjects in each of the analysis populations described in Section 6 will be provided by treatment and overall.

The end of study record will be summarized. This display will show the number and percentage of subjects who completed or withdrew from the study, including primary reason for study withdrawal by cohort and for all subjects.

The list of end of study record will be provided for all subjects. The listing will include study day when subjects discontinue study as well as the reason of subject prematurely withdraw from the study.

## 10.2. Protocol Deviations

Protocol deviations will be reviewed by study team. Only protocol deviations classified as not "Excluded from protocol deviation analysis reporting" will be summarized and listed.

An additional listing of inclusion/exclusion deviations will also be provided.

### **10.3.** Demographic and Baseline Characteristics

The demographic characteristics e.g., age, race, ethnicity, sex, baseline height, and baseline body weight will be summarized and listed. Age, height and weight will be summarized using the mean, standard deviation, minimum, median, and maximum. In addition, country will be included in demographic summary. And age will also be categorized and summarized by <18, 18-64, 65-74, and >74 for Development of Safety Update Report (DSUR). The count and percentage will be computed for sex and ethnicity. A summary of country and age category of 18-64, 65-84, and  $\geq$ 85 will be provided for EU Clinical Trials Register.

Race will be summarized and listed.

Disease history and characteristics, time since initial diagnosis in months, stage at initial diagnosis, date of initial diagnosis will be listed. Separate summaries of disease characteristics at initial diagnosis and screening will be provided.

Substance use, including smoking history, and alcohol use and caffeine use, will be listed.

Prior anti-cancer therapies will be summarized and listed. Prior cancer related surgeries will be summarized and listed. Medical conditions present at screening will be listed.

Summary of baseline ECOG performance status and HER3 and NRG1 status will be provided.

## 10.4. Concomitant Medications

Concomitant medications will be coded using GSK Drug coding dictionary, summarized, and listed. The summary of concomitant medications will show the number and percentage of subjects taking concomitant medications by Ingredient. Multi-ingredient products will be summarized by their separate ingredients rather than as a combination of ingredients. Anatomical Therapeutic Chemical (ATC) classification Level 1 (Body System) information will be included in the dataset created but will not appear on the listing or summary.

Concomitant medications will be summarized separately for medications with onset date within the on-therapy period and for medications with onset date within the pre-therapy period. Note: In order to be considered a concomitant medication, the concomitant medication must have been taken at some point during the on-therapy window.

